#### **12.5.2.5 Overall survival**

OS is defined as the interval between the date of death and the date of randomization/treatment assignment (Arm 4). Patients will be censored at the last time of contact if death has not been confirmed at the time of the analysis. OS will be analyzed using a log-rank test with a term for treatment assignment. In addition, Kaplan-Meier curves will be produced separately for each treatment group. The analysis will be completed for the ITT and Per-Protocol populations.

#### **12.5.2.6 Burden of Repeat TURBT**

Defined as the proportion of patients with no repeat TURBT vs 1 TURBT vs 2 TURBT vs 3 TURBT etc within 12 months since randomization, within 18 months since randomization, and within 24 months since randomization.

#### **12.5.2.7 Time to Cystectomy**

Defined as the time from randomization to cystectomy.

#### **12.5.2.8 Immune Response**

Section 10.2.1 details how samples are run in duplicate or triplicate using ICS via flow cytometry or ELISPOT. The first step in the analysis of immunologic response will be to form the subject average across the duplicate or triplicate measurements recorded at each time point. In situations where only one measurement is obtained, the single value will be used in the analysis. If any values are in the range (0,1) inclusive, a value of 0.5 will be used in the analysis of count information on the log10 scale.

The observed and log10 transformed values will be summarized for each visit. In addition, the change from baseline will also be summarized descriptively. At each visit and for the last available visit, a sign-rank test will be used to evaluate the null hypothesis that the change from baseline is centered at zero separately for each of the dosing groups. Similarly, a Wilcoxon rank-sum test will be used to evaluate the null hypothesis that the observed and change from baseline values have a similar location ((i.e. median) between the low and high dose groups.) A 95% CI for the ratio of the differences geometric mean will be obtained by back-transforming the 95% non-parametric CI for the difference in log10 analysis. For the purposes of identifying the most important comparison, the analysis of the last assessment will be considered the primary analysis with other time points considered secondary analyses. Additionally, a repeated measures analysis will be completed modeling log10 transformed values as a function of visit, treatment, and a visit

by treatment interaction. Model results may not be reported if convergence is unattainable because of the small sample size.

These analyses will be completed using the ITT and Per-Protocol populations.

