## 1.2 Rationale for Vesigenurtacel-L Development

The hypotheses behind the development of vesigenurtacel-L (HS-410), a therapeutic vaccine, to treat urothelial cancer of the bladder are as follows:

(1) A range of tumor-associated antigens (survivin, LAGE-1, MAGE-A3, MAGE-A11, and PRAME) have been identified in bladder cancer, and it is postulated that treatment with BCG therapy provides the innate immune system with a warning signal to induce and direct an acquired immune response against such antigens. However, BCG therapy is accompanied by a high failure rate and significant side effects, which limit its clinical application. The clinical response to BCG might be improved through concurrent enhancement of tumor immunogenicity by concomitant administration of a vaccine, such as vesigenurtacel-L, during standard BCG therapy.

(2) Secreted gp96-Ig from vesigenurtacel-L combines adjuvant activity with polyvalent peptide specificity. Vesigenurtacel-L activates dendritic cells (DC), natural killer (NK) cells, and cytotoxic T lymphocytes (CTL). Tumor cells can be killed by NK cell-specific mechanisms, by promiscuous killing by CD8+ CTL through NKG2D, and by major histocompatibility complex (MHC)-restricted CD8+ CTL activity. The activation of DC and NK cells by vesigenurtacel-L may also counteract the generation of immunosuppressive CD4+ regulatory cells.

(3) Vesigenurtacel-L also stimulates antigen cross presentation via the CD91 receptor, Toll-like receptor (TLR) 2 and TLR4 on DC and macrophages. Allogeneic tumor cells are likely to share public tumor antigens in analogy to melanoma. Therefore, allogeneic, gp96-secreting tumor cells used as a vaccine (such as vesigenurtacel-L) are expected to generate NK cell and CTL activity to the patient's autologous tumor.

(4) BCG activates innate immune receptors, primarily TLR, within the endothelial lining of the bladder following intravesical administration. Activation of these innate receptors contributes to the local production of inflammatory cytokines, including IL-1 $\beta$  and TNF $\alpha$ , which provide an inflammatory signal leading to upregulation of the local microvascular endothelium within the bladder wall, including expression of selectin ligands and integrins, such as ICAM-1 and VCAM-1.

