#### **3.4.2 Secondary Endpoints**

- Safety of the combination of vesigenurtacel-L and BCG (Phase 2 only)
- Safety of high dose vesigenurtacel-L monotherapy (Phase 2 only)
- Proportion of patients with recurrence at 3, 6, 12, 18, and 24 months
- Proportion of patients with progressive disease at 3, 6, 12, 18 and 24 months
- Disease-free survival (DFS) at 3, 6, 18, and 24 months
- Overall DFS
- Overall Survival (OS)
- Proportion of patients undergoing post-treatment TURBT or fulguration by 12 and 24 months
- Proportion of patients undergoing cystectomy by 12 and 24 months
- Proportion of patients with immunologic response of PBMCs via intracellular cytokine staining (ICS) by flow cytometry and/or ELISPOT on CD8+ cells after receiving vesigenurtacel-L treatment as compared to baseline

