7.3 Exploratory Analyses

All primary and secondary efficacy endpoints will be reanalysed in the Per-protocol population.

If available in a suitable timeframe before reporting, immunologic response data will be listed in the CSR. If applicable, summaries and exploratory analyses will be specified in a separate analysis plan and presented in a separate report.

The following endpoints will be analysed:

- immunologic response of PBMCs,
- total PBMC counts by flow cytometry,
- evaluation of tumour tissue obtained from pre-treatment resection for antigen expression by immunohistochemical analysis,
- evaluation of tumour tissue obtained from repeat biopsy, if clinically indicated, for presence of infiltrating T-lymphocytes,
- T cell receptor sequencing of peripheral blood T cells before and during the course of treatment
- Tissue immune cell infiltration, and inflammatory cytokine levels in urine

8 Safety Analyses

Safety comparisons will be performed on all patients who received at least one dose of experimental treatment in both phases of the study. The safety variables to be analyzed include vital sign measurements, AEs, ECGs, routine hematology, coagulation factors, serum chemistry, urinalysis, and deaths. Unless otherwise noted, safety variables will be tabulated by descriptive statistics (n, mean, median, SD, minimum, and maximum; or n and percent) using the Safety Population. When calculating the incidence of adverse events, or any sub-classification thereof by treatment, time period, severity, etc., each subject will only be counted once and any repetitions will be ignored; the denominator will be the total population (or treatment group, as applicable) size. A descriptive summary of all Treatment emergent adverse events (TEAEs) by system organ class and preferred term will be provided.

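### The immune-response section names no vaccine-versus-placebo contrast, so its two named tests cannot separate a vaccine effect from a BCG effect

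*Protocol*

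**What the plan says.** **The endpoint.** Protocol 3.4.2 defines it as the proportion of patients with a response by intracellular cytokine staining and/or "ELISPOT on CD8+ cells after receiving vesigenurtacel-L treatment as compared to baseline". Protocol 10.2.1 counts a patient as a responder when IFNγ-positive CD8+ T cells more than double from that patient's own baseline.

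**The named tests.** Protocol 12.5.2.8 tests whether "the change from baseline is centered at zero separately for each of the dosing groups", then tests whether values "have a similar location ((i.e. median) between the low and high dose groups". The last assessment is the main time point.

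**The model.** The same section adds a repeated-measures model of log10 "transformed values as a function of visit, treatment, and a visit"-by-treatment interaction. It names no contrast from this model and adds: "Model results may not be reported if convergence is unattainable because of the small sample size". On populations it says: "These analyses will be completed using the ITT and Per-Protocol populations". ITT is all randomized patients, so it includes Arm 3.

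**Other relevant text.** Protocol 12.1 presents binary secondary endpoints as odds ratios with 95% CIs, without restating the reference group. Protocol 12.5.2.9 compares responders with non-responders across all four arms, which is not a comparison by treatment. SAP 5.5 confines p-values to the primary analysis. SAP 7.3 says: "If available in a suitable timeframe before reporting, immunologic response data will be listed in the CSR". It leaves any summaries and exploratory analyses to a separate plan and report.

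**The concern.** In Arms 1 and 2, change from baseline is the joint result of BCG, vaccine and time. Protocol 1.2 postulates that "treatment with BCG therapy provides the innate immune system with a warning signal to induce and direct an acquired immune response" against tumour-associated antigens. Those it lists include survivin, LAGE-1 and MAGE-A3, and the assay cocktail in Protocol 10.2.1 contains survivin, LAGE-1s and MAGE-A3. On the protocol's own reasoning, BCG alone could move the readout.

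The low-versus-high comparison does not resolve this. Both groups receive BCG, so the BCG effect drops out, but so does any vaccine effect that is equal at the two doses.

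Two wrong readings are therefore open. An inert vaccine could look immunogenic at both doses, and a vaccine equally active at both doses would show no difference between them. The randomized group that settles the matter is already being sampled.

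**Working it through.** **1. What each named comparison estimates.** Let B be the mean log10 change due to BCG and time, and V1 and V2 the added vaccine effects at low and high dose.

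| Comparison | Estimates | Named in 12.5.2.8? |
|---|---|---|
| Arm 1 against its own baseline | B + V1 | yes |
| Arm 2 against its own baseline | B + V2 | yes |
| Arm 2 minus Arm 1 | V2 − V1 | yes |
| Arm 1 minus Arm 3 | V1 | no |
| Arm 2 minus Arm 3 | V2 | no |

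Only the last two rows isolate the vaccine.

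**2. Whether Arm 3 can supply the contrast.** One Phase 2 schedule of events (Protocol 6.2.1) covers every arm, with immune samples at Baseline and Weeks 7, 13, 28 and 56. Timing does not separate the two agents. BCG and study product are both given at Weeks 50 to 52, so the Week 56 sample follows both by about four weeks.

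**3. Inputs for the illustration.** From the documents: 69 evaluable patients in three arms, 69/3 = 23 per arm (SAP section 4). The documents give no power or effect size for the immune endpoint. Their only power figure is 80% for the primary endpoint. It reproduces at 23 per arm (80.8% by exact one-sided Fisher test, 60% versus 90%, alpha 0.10), but nothing below depends on it. Assumed here: normally distributed change in log10 units, two-sided 0.05, an inert vaccine (V1 = V2 = 0), and a BCG shift d of 0.3, 0.5 or 0.8 SD of the change.

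**4. Rejection rates with an inert vaccine, 23 per arm** (simulation, 4,000 trials per setting).

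| d | Sign-rank, one vaccine arm | Sign-rank, at least one of two arms | Low vs high | High dose vs placebo |
|---|---|---|---|---|
| 0.3 SD | 26% (repeat run 27%) | 47% | 5% | 5% |
| 0.5 SD | 60% (62%) | 85% | 4% | 5% |
| 0.8 SD | 94% (94%) | 99.8% | 4% | 4% |

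With 15 usable patients per arm the single-arm rates are 18%, 42% and 80%; with 25 they are 28%, 65% and 96%. The placebo comparison stays at 4 to 5% throughout.

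Large-sample check: power ≈ Φ(d × √(n × 3/π) − 1.96). With n = 23 the root is 4.69, so d = 0.3, 0.5 and 0.8 give Φ(−0.55), Φ(0.38) and Φ(1.79), that is 29%, 65% and 96%. These are close to the simulation and slightly above it, as expected at this n.

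**5. Power of the missing contrast.** A rank-sum test of 23 versus 23 has about 35%, 71% and 90% power for true vaccine effects of 0.5, 0.8 and 1.0 SD. It is informative for large effects only, which favours reporting an estimate with its interval.

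**6. Responder proportions have the same problem.** With mean log10 change m and SD s, the chance of more than doubling is 1 − Φ((log10 2 − m)/s), with log10 2 = 0.301. Taking s = 0.3 as an assumption, 16% respond when m = 0, 25% when m = 0.1 and 37% when m = 0.2. For m = 0 the figure runs from 7% (s = 0.2) to 27% (s = 0.5). A responder proportion in a vaccine arm cannot be interpreted without the placebo proportion beside it.

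**The case against.** The strongest reply is that the plan already contains routes to the placebo comparison.

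- **Repeated-measures model.** It is run in ITT, which includes Arm 3, and may be dropped only if it fails to converge. This stands: a vaccine-versus-placebo contrast can be drawn from it. But none is named, and the model is additional to the named tests.
- **Odds-ratio rule in Protocol 12.1.** The responder proportion is a binary secondary endpoint, and the primary odds ratios in that section are relative to control. A placebo comparison is fairly implied. Protocol 12.5.2.9 supports this, because it treats responder status as determined in all four arms. Against that, the endpoint is worded for vaccine recipients, and Protocol 12.5.2 opens by assigning the secondary parameters to Kaplan-Meier methods.
- **Homogeneity tests in Protocol 12.1.** Rank-sum and Fisher tests between treatment groups are named, but in the paragraph on exploratory endpoints and for no stated pair.
- **Biology.** The BCG effect is a postulate. Protocol 1.2 describes BCG acting locally in the bladder and credits circulating antigen-specific CD8+ cells to the vaccine. The assay has antigen-specific conditions and controls, and Arm 4 receives vaccine without BCG. These limit the confounding. They do not remove it, because the antigen lists overlap and Arm 4 is non-randomized and high dose only.
- **SAP.** It would produce no p-values for this endpoint, so the significance rates above describe the Protocol's tests and not SAP output. It also defers summaries to a separate plan that is not among the documents, so that plan's contrasts cannot be presumed absent.

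A reader might infer that placebo is never compared, or that a BCG effect will be reported as a vaccine response. The documents support neither: routes to the comparison exist, and a BCG effect on this assay is not shown.

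**Conclusion.** The point holds in a limited form. The two tests named in Protocol 12.5.2.8 cannot separate vaccine from BCG, and nowhere do the documents name the Arm 1 or Arm 2 versus Arm 3 contrast for immune response or make it the leading comparison. A within-arm rise could be misread as a vaccine response.

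The size is illustrative. The false-attribution rates of about 26%, 60% and 94% rest on assumed BCG shifts, normal changes, 23 patients per arm and a two-sided 0.05 level that the documents do not set for this endpoint. If BCG does not move the assay, the rate is the nominal 5%. The algebra in the first table needs none of these assumptions.

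This is a secondary biomarker endpoint in a trial that the SAP calls exploratory, so the primary analysis is untouched. The change should still be made, because the better comparison is randomized and its samples are already planned.

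**What to change.** 1. In Protocol 12.5.2.8, make Arm 1 versus Arm 3 and Arm 2 versus Arm 3 the leading comparisons. Report the rank-based shift in log10 change from baseline and the difference in responder proportions, each with a 95% CI. Estimates without p-values agree with SAP 5.5.
2. Label the within-arm changes and low versus high dose as supportive, and Arm 4 as descriptive.
3. State which contrasts are to be drawn from the repeated-measures model.
4. Reword the endpoint in Protocol 3.4.2, and the matching text in the synopsis, objectives and SAP, from response after vesigenurtacel-L to response *after study product*, so that Arm 3 is plainly included.
5. Carry the same contrasts into the SAP or the separate immune analysis plan that SAP 7.3 foresees, before unblinding.

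Cost: wording in the Protocol and in one analysis plan, and two extra contrasts. No new samples are needed, because Arm 3 already follows the common Phase 2 sampling schedule.

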### **3.3 Number of Subjects**

Approximately 110 patients will be enrolled from up to 20 clinical trial centers. In Phase 1, 10 patients will be enrolled in a single cohort given treatment with monotherapy low dose vesigenurtacel-L. In Phase 2, 25 patients will be enrolled in each of four arms: low dose vesigenurtacel-L in combination with BCG, high dose vesigenurtacel-L in combination with BCG, placebo in combination with BCG, and high dose vesigenurtacel-L monotherapy (100 patients total).

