### 6.2.3.1 Phase 2 Baseline Assessments (Day -3 to Day 1)

The following activities may be performed within three days of enrollment/randomization or on Day 1 prior to enrollment/randomization:

- Update of medical history including concomitant medications
- Blood and urine collection for immune monitoring
- Physical examination (symptoms, weight, vital signs only if screening exam performed more than three days prior to first dose)
- Hematology, chemistry with LDH, and dipstick urinalysis (unless screening labs obtained within three days of first dose)
- Urine or serum pregnancy test for female patients of childbearing potential (unless screening labs obtained within three days of first dose)

- Autoimmune Labs (ANA, TSH, ESR, and C-reactive protein are required; RF, T3, T4, and thyroid antibodies if clinically indicated)
- Autoimmune Phenomena – Assessment of adult autoimmune system disorders (including: eye exam for dry eyes, lymph node and joint assessment for swelling, and skin exam for vitiligo and rash)

Once the patient has met all of the eligibility requirements for the study, patients who will receive BCG will be randomized (treatment assigned within IWRS). Each patient will be considered enrolled in the study at the time of first dose.

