The frequency of IFN $\gamma$  producing CD8+ cells is thought to mirror the frequency of cytotoxic CD8+ cells. However, cytotoxicity is primarily mediated by perforin and granzymes following granule exocytosis. In some instances IFN $\gamma$  secretion and granule exocytosis are uncoupled. Therefore, the direct measurement of grzB secretion by ICS may provide a more direct readout for antigen-specific granule exocytosis and cytotoxicity. For clinical efficiency it may be important to detect both IFN $\gamma$  secretion and grzB exocytosis. Antigen specificity of the ICS response will be evaluable by comparing responses generated using the various stimulator cell populations and specific shared bladder cancer antigens as indicated. This will also enable separation of the ‘allo-antigen’ specific response with the potential parent cell line tumor-antigen-specific response. Positive responses will be defined as a greater than two-fold increase in the number of IFN $\gamma$  positive CD8+ T cells compared to baseline.

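### The between-group immune-response analyses in Protocol 12.5.2.8 do not adjust for the baseline sample already scheduled; adding it as a covariate would probably gain precision, by an amount that depends on a correlation the documents do not give

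*Protocol*

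**What the plan says.** Protocol 12.5.2.8 sets out four layers of analysis for the immune assays.

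- Observed values, log10 values and change from baseline are summarised at each visit.
- Within each dose group, a signed-rank test asks whether the "change from baseline is centered at zero separately for each of the dosing groups".
- Between the low and high dose groups, "a Wilcoxon rank-sum test will be used to evaluate the null hypothesis that the observed and change from baseline values have a similar location". A 95% CI for a geometric-mean ratio is back-transformed from a non-parametric interval on the log10 scale. Among time points, "the analysis of the last assessment will be considered the primary analysis".
- In addition, a repeated-measures model takes log10 "transformed values as a function of visit, treatment, and a visit"-by-treatment interaction. The section adds: "Model results may not be reported if convergence is unattainable because of the small sample size".

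No baseline covariate is named, and the section does not say whether the baseline visit is one of the modelled visits.

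The baseline data are planned. The Phase 2 schedule (Protocol 6.2.1) has immune samples at Baseline and at Weeks 7, 13, 28 and 56, and Protocol 6.2.3.1 lists "Blood and urine collection for immune monitoring" among the baseline activities. On arm size, Protocol 3.3 says: "In Phase 2, 25 patients will be enrolled in each of four arms".

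The SAP adds little. Section 7.3 lists the immune data if they arrive in time and leaves summaries and exploratory analyses to a separate plan. Section 5.5 confines p-values to the primary endpoint and presents other endpoints as estimates with 95% CIs.

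**The concern.** In a small randomised comparison of a noisy assay, the patient's own baseline is usually the cheapest source of precision. With 25 per arm, the baseline mean difference between two arms has a standard error of sqrt(2/25) = 0.28 baseline SDs by chance alone. A comparison of observed values carries a fraction of that difference into the result. A comparison of change scores subtracts all of it, which generally over-corrects. Adjustment removes the fraction that the data support.

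Neither reading of the repeated-measures model does this.

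- If baseline is not a modelled visit, the visit-specific treatment contrasts compare raw post-baseline values.
- If baseline is a modelled visit, then with complete data and an unstructured covariance the interaction contrast has exactly the precision of a change-score comparison.

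The text leaves the choice open, so it could be made after the data are seen. At stake is the width of the intervals for the between-group immune estimates. Under SAP 5.5 those intervals, not p-values, are what would be reported.

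**Working it through.** **The plan's own figure.** There is none for this analysis: the documents give no SD, correlation or power for the immune assays. The only power statement concerns 1-year disease-free survival (60% against 90%, one-sided 0.10, 23 evaluable per arm). Full enumeration of Fisher's exact test gives 80.8% against the stated 80%, so that figure reproduces, but it has no bearing here.

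**Inputs.** n = 25 per arm (Protocol 3.3). Rho, the correlation of baseline with post-baseline log10 values, is assumed at 0.3, 0.5 and 0.7. Baseline and post-baseline SDs are first assumed equal.

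**Formulas.** For a between-group difference in means at one post-baseline time point, relative to the raw comparison:

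- raw values: 1
- change from baseline: 2(1 - rho)
- baseline-adjusted: 1 - rho^2

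The saving is therefore rho^2 against raw values. Against change it is 1 - (1 - rho^2)/[2(1 - rho)] = (1 - rho)/2. Estimating one covariate at 25 per arm multiplies the adjusted variance by 1 + 1/(2n - 4) = 1 + 1/46 = 1.022.

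| rho | Raw | Change | Adjusted | Saved vs raw (net) | Saved vs change (net) |
|---|---|---|---|---|---|
| 0.3 | 1 | 1.4 | 0.91 | 9% (7%) | 35% (34%) |
| 0.5 | 1 | 1.0 | 0.75 | 25% (23%) | 25% (23%) |
| 0.7 | 1 | 0.6 | 0.51 | 49% (48%) | 15% (13%) |

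Example of a net figure: at rho 0.3, 1 - 0.91 x 1.022 = 0.07 against raw, and 1 - (0.91 x 1.022)/1.4 = 0.34 against change. A simulation with 20,000 replicates per rho at 25 per arm gave 7%, 23% and 48% against raw and 33%, 24% and 12% against change.

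The two ranges run in opposite directions: a low rho favours raw values over change, and a high rho favours change over raw values. At rho 0.5, before the covariate cost, the saving is equivalent to raising 25 per arm to 25/0.75 = 33.

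**Break-even against raw values.** Adjustment pays when (1 - rho^2) x 47/46 < 1, that is rho^2 > 1/47, or rho above about 0.15.

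**Unequal SDs.** Let k be the baseline SD divided by the post-baseline SD. The change variance becomes 1 + k^2 - 2 rho k, which exceeds 1 - rho^2 by (k - rho)^2. The saving against raw values stays at rho^2. The saving against change is (k - rho)^2/(1 + k^2 - 2 rho k), which is zero when k = rho. Before the covariate cost:

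| k | rho 0.3 | rho 0.5 | rho 0.7 |
|---|---|---|---|
| 0.25 | 0.3% | 7.7% | 28.4% |
| 0.50 | 4.2% | 0% | 7.3% |
| 0.75 | 18.2% | 7.7% | 0.5% |
| 1.00 | 35% | 25% | 15% |

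These formulas describe mean differences on the log10 scale. For the rank-sum tests they are only a guide.

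**The case against.** The strongest reply is that the plan does use baseline, and that little hangs on the model. Much of this stands.

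- **Baseline is used elsewhere.** A reader might infer that the plan ignores baseline altogether, or that its paired tests waste it. The documents do not support that. The only paired test is the within-group signed-rank test, which works on change from baseline. The rank-sum tests criticised here compare independent groups, and one of the two versions uses change. The listed secondary endpoint is a responder proportion, already referenced to baseline: "Positive responses will be defined as a greater than two-fold increase in the number of" IFN-gamma-positive CD8+ T cells compared with baseline. The variance figures do not apply to the signed-rank tests or to that proportion.
- **The model is supplementary.** It follows the rank tests, no decision rule depends on it, and SAP 7.3 defers immune summaries to a plan that is not available here. That plan may deal with baseline. Until it does, Protocol 12.5.2.8 is the only specification.
- **Convergence.** The protocol already doubts that the model will fit, and baseline-by-visit terms add parameters. But if baseline is currently a modelled visit under an unstructured covariance (the structure is not stated), five time points need 5 x 6/2 = 15 covariance parameters. Moving baseline to the covariate side leaves four visits and 4 x 5/2 = 10.
- **Floor-limited counts.** Protocol 12.5.2.8 sets values from 0 to 1 to 0.5 for the log10 analysis, so it expects results near the floor. That is a good reason to keep the rank tests at their planned standing and not to demote them to sensitivity analyses.
- **Missing baselines.** A scheduled sample is not an obtained one. Conditioning on baseline drops patients without one unless the model handles this.

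**Conclusion.** The point holds as a modest improvement in precision and a needed clarification. No between-group immune analysis in Protocol 12.5.2.8 adjusts for baseline, and the role of the baseline visit in the model is unstated. With equal SDs and rho between 0.3 and 0.7, adjustment would save about 7% to 48% of the variance against raw values and about 34% down to 13% against change scores, net of the covariate cost at 25 per arm.

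Three stronger readings are not supported. First, 9% to 49% is not a known loss: it is rho^2 for an assumed range of rho, and it concerns raw values only. Secondly, adjustment does not win at every positive correlation: it fails to pay against raw values below rho of about 0.15, and it gains nothing against change when the SD ratio equals rho. Thirdly, neither the primary endpoint nor the two-fold responder endpoint is affected.

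**What to change.** In Protocol 12.5.2.8, and in the separate immune plan that SAP 7.3 foresees, say how the baseline visit enters the model and adopt one of two forms:

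1. Model post-baseline log10 values on log10 baseline, visit, treatment and visit-by-treatment, with baseline-by-visit if the model converges.
2. Keep baseline in the response vector and constrain baseline means to be equal across the randomised Arms 1-3. This also retains patients without a baseline sample. The constraint should not extend to Arm 4, which is not randomised.

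Report the adjusted geometric-mean ratios with 95% CIs alongside the planned rank tests. The within-group tests and the responder definition stay as they are.

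The cost is one or a few degrees of freedom and a short change to the model text. No additional sample or visit is needed.
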